2.2.4. Exploratory Objectives

The exploratory objectives are:

- 1. To identify potential biomarkers related to response to concurrent cetuximab and nivolumab in patients with recurrent and/or metastatic HNSCC.
- 2. To determine a quantitative radiomics based on CT and/or PET images as a prognostic biomarker in recurrent or metastatic HNSCC.

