9.1.4. Duration of Follow-up

Study Number: MCC 19178

For this protocol, all patients, including those who discontinue protocol therapy early, will be followed for response until progression and for survival for 2 years from the End of Treatment. Patients that discontinue protocol therapy early without documented disease progression may have their scans performed per standard of care. All patients must also be followed through completion of all protocol therapy. Patients removed from study for unacceptable adverse events will be followed until resolution or stabilization of the adverse event.

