10.1.2. Phase II Study

Primary Objectives:

Phase II Cohort A: To test if the overall survival rate of concurrent cetuximab and nivolumab in patients who had progressed on at least one prior line of treatment for their recurrent and/or metastatic HNSCC exceeds that of the historical data, which has an estimated one-year survival rate of 36%.

Cohort A: We will assume 36% one-year overall survival based on the historical data from nivolumab monotherapy. With our expected 56% one-year overall survival after the combined treatment with both cetuximab and nivolumab, we will need to enroll 45 patients to reach 90% power to see a statistically significant difference ($P \le 0.05$) in overall survival. 45 evaluable patients will be treated at the MTD. In order to be considered evaluable, patients

must complete the lead-in period and receive the C1D1 doses of cetuximab and nivolumab. Non-evaluable subjects will be replaced.

IND#: Exempt

Phase II Cohort B: To test if the 1-year overall survival rate of concurrent cetuximab and nivolumab in patients who has not had any prior treatments for their recurrent and/or metastatic HNSCC exceeds that of the historical data, which has an estimated one-year survival rate of 46%.

Cohort B: We will assume 46% one-year overall survival based on the historical data from pembrolizumab monotherapy. With our expected 66% one-year overall survival after the combined treatment with both cetuximab and nivolumab, we will need to enroll 43 patients to reach 90% power to see a statistically significant difference ($P \le 0.05$) in overall survival. 43 evaluable patients will be treated at the MTD. In order to be considered evaluable, patients must complete the lead-in period and receive the C1D1 doses of cetuximab and nivolumab. Non-evaluable subjects will be replaced.

The sample size was obtained for the one-sample log-rank test from PASS15, with the assumption that accrual will take one year with one-year follow-up.

Secondary Objectives:

Study Number: MCC 19178

 To estimate response rate of patients treated with concurrent cetuximab and nivolumab who have recurrent and/or metastatic HNSCC.

The response rate will be estimated using binomial theory with Wilson's method for the 95% confidence interval.

 To estimate progression-free survival of patients treated with concurrent cetuximab and nivolumab who have recurrent and/or metastatic HNSCC.

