The median and 1-year progression-free survival rates will be estimated from the Kaplan-Meier curve with its 95% confidence interval.

• To evaluate the toxicity of the cetuximab and nivolumab combination in this patient population.

The toxicity data will be provided in a table by major toxicity category and for the highest toxicity grade for the patient.

Exploratory Objectives:

 To identify potential biomarkers related to response to concurrent cetuximab and nivolumab in patients with recurrent and/or metastatic HNSCC.

Exploratory analysis to assess the association of potential biomarkers with disease response will be made using logistic regression.

 To determine a quantitative radiomics based on CT and/or PET images as a prognostic biomarker in recurrent or metastatic HNSCC

Exploratory analysis to assess the association of potential radiomics signatures with disease response will be made using logistic regression.

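### The radiomics objective is prognostic, but its only planned analysis is logistic regression on response, so radiomics is never related to OS or PFS

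*Combined protocol and SAP*

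**What the plan says.** The second exploratory objective in section 2.2.4 is: "To determine a quantitative radiomics based on CT and/or PET images as a prognostic biomarker in recurrent or metastatic HNSCC". The synopsis and section 10.1.2 state it in the same terms. The first exploratory objective is a different one: biomarkers related to response to the combination.

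Under Exploratory Objectives, section 10.1.2 gives one analysis sentence for each. For the response biomarkers: "Exploratory analysis to assess the association of potential biomarkers with disease response will be made using logistic regression". For radiomics: "Exploratory analysis to assess the association of potential radiomics signatures with disease response will be made using logistic regression". Only the predictor changes; outcome and model are the same.

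Survival and progression data are collected in any case. OS is the primary endpoint of both phase II cohorts. Under section 9.1.4 all patients are "followed for response until progression and for survival for 2 years from the End of Treatment". PFS is a secondary endpoint, and its whole analysis is: "The median and 1-year progression-free survival rates will be estimated from the Kaplan-Meier curve with its 95% confidence interval". No regression model for a time-to-event outcome appears anywhere in the supplied text.

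Section 6.2 governs image handling. At the coordinating centre (Moffitt), baseline, response and historic images are evaluated for all evaluable patients. From the other two sites, images are submitted only for patients with a response, in order to confirm it. Footnote d of the study calendar says that historic imaging obtained under section 6.2 is meant to serve the exploratory objectives.

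**The concern.** A prognostic marker is conventionally one related to the later course of the disease, that is, to survival or progression. An odds ratio for response relates radiomics to tumour shrinkage on this regimen, which is at best a surrogate for that course. The protocol keeps the two ideas apart: it gives them separate objectives, and section 1.1.2 treats response, risk of death and prognosis in HPV-related disease as distinct matters. The likeliest explanation is that the analysis sentence for the first objective was reused and the outcome was not changed.

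At stake is whether the trial can speak to its own radiomics question with data it already holds. If survival is added only after the data are seen, the outcome will have been chosen post hoc, which weakens even an exploratory finding.

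**Working it through.** **1. Objective against analysis**

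| Exploratory objective | What it asks | Outcome analysed | Model |
|---|---|---|---|
| Biomarkers | Relation to response | Response | Logistic |
| Radiomics | Prognosis | Response | Logistic |

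The first row is consistent; the second is not. Nothing else in the supplied text closes the gap. The imaging text covers acquisition and response review. The body of section 8.3 was not available, but its headings in the table of contents list no radiomics section.

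**2. The plan's sample sizes, to fix the planning model**

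Inputs from section 10.1.2. Cohort A: 36% at one year under the null (nivolumab alone) against 56% expected, with the size stated as "we will need to enroll 45 patients to reach 90% power". Cohort B: 46% against 66%, 43 patients, 90% power. Both use a one-sample log-rank test with P ≤ 0.05, one year of accrual and one year of follow-up. I assume exponential survival and uniform accrual.

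n = (z_α√p0 + z_β σ1)² / (p0 − p1)²

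Here p1 is the probability of death under the alternative, p0 the expected null cumulative hazard under the alternative, and σ1 the standard deviation under the alternative.

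- A: p1 = 0.575, p0 = 1.013, σ1 = 0.983. At one-sided 0.05, (1.645 × 1.0066 + 1.282 × 0.983)² / 0.438² = 44.3, so 45.
- B: p1 = 0.460, p0 = 0.860, σ1 = 0.852. (1.645 × 0.927 + 1.282 × 0.852)² / 0.400² = 42.9, so 43.

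Both planned sizes are reproduced. The plan does not state sidedness; with the same formula, two-sided 0.05 would give 54.4 and 53.0 before rounding.

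**3. Expected deaths**

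P(death) = 1 − (S − S²)/λ, with λ = −ln S and S the one-year survival.

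- A at 56%: λ = 0.580; 1 − (0.56 − 0.3136)/0.580 = 0.575; × 45 = 25.9.
- B at 66%: λ = 0.416; 1 − (0.66 − 0.4356)/0.416 = 0.460; × 43 = 19.8.
- Total 45.7, about 46. At the null rates: 34.9 + 29.2, about 64.

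Follow-up for two years after End of Treatment can only add deaths. If PFS counts progression or death, it has at least as many events as OS.

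**4. Expected responders**

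The plan gives no target response rate. As an assumption I use the 10% to 40% that section 1.1.1 cites for existing agents, and the 13% that section 1.1.4 cites for nivolumab.

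- 88 × 0.10 = 8.8
- 88 × 0.13 = 11.4
- 88 × 0.40 = 35.2

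**5. Rough information for one standardised feature, all 88 patients**

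For logistic regression it is about N r(1 − r); for a Cox model it is about the number of deaths.

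- 10%: 88 × 0.10 × 0.90 = 7.9, or 17% of 45.7
- 13%: 88 × 0.13 × 0.87 = 10.0, or 22%
- 40%: 88 × 0.40 × 0.60 = 21.1, or 46%

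In Cohort B alone at 40% it is about half: 43 × 0.24 = 10.3 against 19.8.

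**6. What image submission does to these counts**

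The figure of 88 needs baseline images from every patient. With coordinating-centre images only, all counts shrink with that centre's share of enrolment, which the documents do not give. Two illustrative shares:

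| Share (assumed) | Patients | Deaths | Responders at 10% to 40% |
|---|---|---|---|
| One half | 44 | 23 | 4 to 18 |
| One third | 29 | 15 | 3 to 12 |

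Using images exactly as submitted is worse than restricting the sample. The outside sites would contribute responders only, so the survival sample is selected on a post-baseline event related to survival. In the response model those sites supply no non-responders, so feature differences between sites can pass for differences by response.

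**The case against.** **The plan names response as the outcome and never defines prognostic.** True, and response could be read as a surrogate. But the protocol has a separate objective for response, so this reading makes the second objective largely repeat the first with a different predictor.

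**A Cox model in a single arm does not establish prognosis either.** This stands. Without a control arm, neither model separates prognostic from predictive value. The Cox model does at least use the outcome to which the objective refers.

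**The numbers are soft.** This stands in part. The response range is assumed, and 88 is an upper bound. A reader might set the smallest detectable effects side by side: for one feature at 80% power and two-sided 0.05, a hazard ratio of about 1.51 per SD with 46 deaths, and odds ratios of 2.71 to 1.84 over response rates of 10% to 40%. These lie on different scales, and the plan sets no test level or power for this analysis, so they are not like for like. The information shares above are approximate for the same reason.

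**Stronger readings that the documents do not support.** A reader might infer that the plan replaces a survival endpoint with a binary one. It does not: OS remains primary and PFS secondary, and nothing bars a further survival analysis. A reader might also infer that the change needs no further data handling. Section 6.2 contradicts that, because no supplied text provides for sending non-responders' scans from the outside sites.

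**Conclusion.** The mismatch is explicit and the point holds. The radiomics objective is prognostic, while its only planned analysis concerns response, so the plan as written does not relate radiomics to OS or PFS.

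The size is approximate. With baseline images from all 88 patients, about 46 deaths are expected, against about 9 to 35 responders (about 11 at a 13% response rate). This rests on the planning survival rates, exponential survival, one year of accrual plus one of follow-up, and response rates of 10% to 40%. With coordinating-centre images only, deaths and responders both fall in proportion to that centre's unstated share of enrolment.

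The importance is low. The objective is exploratory, and no primary or secondary conclusion depends on it. The change is worth making because it is cheap and fixes the outcome before the data are analysed.

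**What to change.** **Section 10.1.2.** Make the radiomics analysis a Cox model of baseline radiomics features on OS and on PFS, stratified by cohort. Keep the logistic model for response as a secondary association. State that a single-arm trial cannot separate prognostic from predictive value.

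**Section 6.2.** Do one of the following, so that the sample is not selected on response:

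- request baseline scans from all evaluable patients at all sites; or
- restrict the radiomics analysis to coordinating-centre patients and say so.

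**Cost.** About one sentence in each section. The first option adds the transfer of scans already acquired, since screening scans are required at every site. The second adds no transfer but gives a smaller sample. Neither needs new patients, visits or scans.

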11. ADMINISTRATION, HANDLING OF DATA, AND SAFETY MONITORING

11.1. PROTOCOL AMENDMENTS

Study Number: MCC 19178

Any changes to the protocol will be made in the form of an amendment and must be approved by the coordinating site IRB before implementation. Any modifications made to the protocol or informed consent document according to local requirements or any other reason may also require approval from sponsoring agencies.

IND#: Exempt

11.2. INFORMED CONSENTS

An investigator will explain to each participant the nature of the study, its purpose, procedures involved, expected duration, and potential risks and benefits. All patients will be informed that participation in the study is voluntary and that they may withdraw from the study at any time, and that withdrawal of consent will not affect their subsequent medical treatment. This informed consent will be given by means of a standard written statement and will be submitted for IRB approval prior to use. No patient will enter the study before informed consent has been obtained. In accordance with the Health Information Portability and Accountability Act (HIPAA), the written informed consent document (or a separate document to be given in conjunction with the consent document) will include a subject authorization to release medical information to the study sponsor and supporting agencies and/or allow these bodies, a regulatory authority, or Institutional Review Board access to the patient's medical information, which includes all hospital records relevant to the study, including the patient's medical history.

11.3. ETHICS AND GOOD CLINICAL PRACTICE

This study must be carried out in compliance with the protocol and Good Clinical Practice, as described in:

- 1. ICH Harmonized Tripartite Guidelines for Good Clinical Practice 1996.
- 2. US 21 Code of Federal Regulations dealing with clinical studies (including parts 50 and 56 concerning informed consent and IRB regulations).
- Declaration of Helsinki, concerning medical research in humans (Recommendations Guiding Physicians in Biomedical Research Involving Human Subjects, Helsinki 1964, amended Tokyo 1975, Venice 1983, Hong Kong 1989, Somerset West 1996).

The investigator agrees to adhere to the instructions and procedures described in it and thereby to adhere to the principles of Good Clinical Practice that it conforms to.

11.4. REGULATORY AUTHORITIES

11.4.1. Institutional Review Board

Information regarding study conduct and progress will be reported to the Institutional Review Board (IRB) per the current institutional standards of each participating center.

11.4.2. Food and Drug Administration

This trial involves an Investigational New Drug (IND) exemption.

11.5. DATA QUALITY ASSURANCE

11.5.1. Data Management

All information will be collected on study-specific CRFs by the study staff at each institution. The necessary forms will be provided to each site by the Coordinating Center.

The completed forms will be forwarded to the Coordinating Center for central review and inclusion in the study dataset with relevant source documentation as outlined in the CRFs. The data submission schedule is as follows:

At the time of registration:

- Registration Form
- Informed Consent Form (signed by the patient)
- Eligibility Checklist
- Source documents related to eligibility.

Within 2 weeks after registration:

- Baseline study CRFs
- Pertinent source documents

Study Number: MCC 19178 IND#: Exempt

Within 2 weeks after 30-day follow-up:

- On-study CRFs
- Pertinent source documents

All study data will be reviewed for completeness and accuracy by the Protocol Chair. The Principal Investigator (or his/her designee) at each respective institution is responsible for review and for ensuring the completeness and accuracy of the data generated by his/her institution. The study data will also be periodically reviewed by the Moffitt Cancer Center Clinical Research Office.

Registration Procedures with Moffitt Clinical Research Network (MCRN) Office

All subjects must be registered with the MCRN Coordinating Center to be able to participate in a trial. The participating site must fax or email the completed study specific eligibility checklist and registration forms, supporting documents and signed informed consent to the Coordinating Center. Unsigned or incomplete forms will be returned to the site. Once documents are received, the MCRN Research Coordinator will review them to confirm eligibility and to complete the registration process. If eligibility cannot be confirmed, the research coordinator will query the site for clarification or additional documents as needed. Subjects failing to meet all study eligibility requirements will not be registered and will be unable to participate in the trial.

Upon completion of registration, the MCRN Research Coordinator will provide the participating site with the study sequence number on the completed registration form (APPENDIX 3).

It is the responsibility of the participating Investigator or designee to inform the subject of the research treatment plan and to conduct the study in compliance with the protocol as agreed upon with Moffitt Cancer Center and approved by the site's IRB.

11.5.2. Meetings and Conference Calls

Scheduled meetings and conference calls will take place as needed with the medical oncology

co-investigators and study personnel involved at the coordinating center and participating sites. In addition, separate meetings will be scheduled and include the protocol principal investigator, study coordinator(s), data manager(s), collaborators, and biostatistician involved with the conduct of the protocol. During these meetings, matters related to the following will be discussed: safety of protocol participants, validity and integrity of the data, enrollment rate relative to expectation, characteristics of participants, retention of participants, adherence to protocol (potential or real protocol violations), data completeness, and progress of data for objectives.

11.5.3. Monitoring and Auditing

Study Number: MCC 19178 IND#: Exempt

Data will be captured in OnCore, Moffitt's Clinical Trials Database. Regulatory documents and case report forms will be monitored internally according to Moffitt Cancer Center Monitoring Policies. Monitoring will be performed regularly to verify data is accurate, complete, and verifiable from source documents; and the conduct of the trial is in compliance with the currently approved protocol/amendments, Good Clinical Practice (GCP), and applicable regulatory requirements.

To obtain access to OnCore, the External Site Coordination (ESC) office Coordinator will supply forms required to be completed by the site staff. Once the completed forms are received, the site coordinator will receive DUO access, logon/password, and information on how to access OnCore. The ESC office will provide OnCore training to the site once initial access is granted and on an ongoing basis, as needed.

Protocol Monitoring Committee (PMC)

The PMC meets monthly and reviews accrual, patterns and frequencies of all adverse events, protocol violations and when applicable, internal audit results.

The Protocol Chair is responsible for monitoring the study. Data must be reviewed to ensure the validity of data, as well as the safety of the participants. The Protocol Chair will also monitor the progress of the trial, review safety reports, and clinical trial efficacy endpoints and to confirm that the safety outcomes favor continuation of the study.

The Protocol Chair will be responsible for maintaining the clinical protocol, reporting adverse events, ensuring that consent is obtained and documented, reporting of unexpected outcomes, and reporting the status of the trial in the continuing renewal report submitted to the IRB and to the trial monitoring review group. Content of the continuing renewal report at a minimum should include year-to-date and full trial data on the following: accrual and eligibility, protocol compliance, treatment administration, toxicity and ADR reports, response, survival, regulatory compliance, and compliance with prearranged statistical goals. The report should be submitted in a timely manner according to the schedule defined by the Moffitt Cancer Center Institutional Review Board.

Regulatory documents and case report forms will be monitored internally according to Moffitt Cancer Center Monitoring Policies. Monitoring will be performed regularly by the MCC Clinical Monitoring Core for accuracy, completeness, and source verification of data entry, validation of appropriate informed consent process, reporting of SAEs, and adherence to the protocol, Good Clinical Practice (GCP) guidelines, and applicable regulatory requirements.

12. COORDINATING CENTER AND SITE RESPONSIBILITIES

12.1. PROTOCOL CHAIR

The Protocol Chair is responsible for performing the following tasks:

 Coordinating, developing, submitting, and obtaining approval for the protocol as well as its subsequent amendments.

IND#: Exempt

- Ensuring that all participating institutions are using the correct version of the protocol.
- Taking responsibility for the overall conduct of the study at all participating institutions and for monitoring the progress of the study.
- Reviewing and ensuring reporting of Serious Adverse Events (SAE).
- Reviewing data from all sites.
- Protocol chair has the authority to stop the study.

12.2. COORDINATING CENTER

Study Number: MCC 19178

The Coordinating Center is responsible for performing the following tasks:

- Ensuring that IRB approval has been obtained at each participating site prior to the first patient registration at that site and maintaining copies of IRB approvals from each site.
- Managing central patient registration.
- Collecting and compiling data from each site.
- Establishing procedures for documentation, reporting, and submitting of AEs and SAEs to the Protocol Chair and all applicable parties.
- Facilitating audits by securing selected source documents and research records from participating sites for audit, or by auditing at participating sites.

